Study Population	
 • 50 years or older • Positive RT- PCR for Sars-Co-V2. • Either asymptomatic or have mild symptoms. Onset of symptoms within no more than 4days • With chronic stable medical conditions: Diabetes Mellitus, or Hypertension, or chronic heart disease.
Study Duration	Total study duration approximately 35 days Screening: 04 days Treatment duration: 14 days Follow-up: 14 days from end of treatment

Number of Sites	02 (two)
Treatment Duration	14 days
Treatment Arms	
Two treatment arms
 
 • Arm A: ViraCide softgels: 3 soft gels, two times every day after breakfast and dinner for 14 days+ SOC Therapy • Arm B: Placebo softgels: 3 soft gels, two times everyday after breakfast and dinner for 14 days + SOC Therapy
Purpose of the study	To study the effectiveness and safety of the Study Drug, ViraCide
	softgels by oral administration compared with placebo softgels in 50 years or older subjects with asymptomatic or mildly symptomatic coronavirus infection (COVID-19) and stable comorbidities.
Objectives	
Primary Objectives
 
1. To evaluate the efficacy of “ViraCide” in the management of mild COVID-19 disease
 
Secondary Objectives
 
1. To evaluate the safety of “ViraCide” in the management of mild COVID-19 disease

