Primary Endpoints	
1. TICI using NEWS Score [Time Frame: First treatment date up to discharge day (PI's discretion as per patients health condition)]
 
The median time in days from the start of treatment with the study drug / placebo to the persistent achievement of all of the following criteria:
 
 • Stopping a fever (which is defined as a decrease in axillary temperature below 37 ° C without the use of anti pyretic drugs); • Respiratory rate <22 /min; • Oxygen saturation (SPO2) > 95% when breathing in atmospheric air. Measured using pulse oximetry • Systolic blood pressure ≤200mmHg • Pulse rate 51-90beats/minute • Is conscious and alert 
[Note: Persistent achievement means the preservation of each of the criteria for at least 7days.]
 
2. TTIC using 7-point ordinal scale
 
3. Rate of progression to severe/critical COVID-19 disease based on NEWS score [Time frame: First treatment date up to 15days]
 
4. Rate of progression to severe/critical COVID-19 disease based on 7-point ordinal scale [Time frame: First treatment date up to 28days]
 
5. Time to COVID-19 nucleic acid testing negativity in oropharyngeal/nasal swab) [Time Frame: First treatment date up to 28days]

Secondary Endpoints	
 1. Incidence of ICU admissions [Time Frame: 28days] 2. Subject survival rate [Time Frame: 28days] 3. Incidence of mechanical ventilation due to COVID-19 infection [Time Frame: First treatment date up to 28days] 4. Change in clinical or laboratory assessment of comorbid condition [Time Frame: First treatment date up to 28days] 5. Percent of participants with worsening comorbid condition [Time Frame: First treatment date up to 28days] 6. Proportion of subjects in the treatment arm who had AE, SAE 7. Proportion of subjects in the placebo arm who had AE, SAE
Subject Selection Criteria	
Inclusion criteria
 
 1. 50 years or older

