	
Note:
 
*Hematology: Complete blood count (CBC); erythrocyte sedimentation rate (ESR)
 
*Biochemistry:
 
 • Random Blood Sugar, • Serum Creatinine • SGOT, SGPT • Alkaline Phosphatase • Bilirubin-Total/Direct/Indirect • Total Proteins/Albumin/Globulin/A:Gratio • Low density lipoprotein (LDL) Cholesterol(Direct) • LDH • Total Cholesterol • Triglycerides • High Sensitive C-reactive protein(HS-CRP) • BUN (Blood Urea Nitrogen) /Urea • Serum Calcium • Serum Sodium • Serum Potassium • Uric Acid 
*X-ray PA view is an optional test at screening. It may be done

	
at any other time during the study if deemed necessary by the Investigator
 
*Urine pregnancy test (for females only) at screening
 
Note: If subject is discharged before Day 15 PI's discretion as per patients health condition, then assessments scheduled for Day 15 will be carried out on the discharge day (as far as possible and those not performed will be noted on appropriate CRF page) and Day 15 visit will be done telephonically.

Standard of Care Therapy	
SOC therapy for coronavirus infection (COVID-19, SARS-CoV-2) has not been developed yet. Treatment will be given as per the discretion of the PI or as per the guidelines issued by the GOI. GOI guidelines can be accessed here: https://www.mohfw.gov.in/

Concomitant Medications Allowed by the Protocol	
 1. Medications for Diabetes Mellitus 2. Medications for hypertension 3. Statins 4. Blood thinners like aspirin at PI discretion 5. Any medication deemed necessary by the PI to manage the AE/SAE 6. Any other medication deemed necessary by the PI to manage a comorbid condition that is not likely to affect the treatment Protocol
Prohibited Concomitant Medications	Any other herbal medicine or dietary supplement
Statistical Analysis	
Sample size of total 112(56 cases in each arm) completed cases needed to assess the study objective at 80% power and 5% level of significance.
 
Considering 10 % dropout total 124 (62 cases in each arm) cases will be enrolled in this study.

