STATISTICAL ANALYSIS PLAN

STUDY TITLE:

A DOUBLE BLIND, RANDOMIZED, PLACEBO CONTROLLED

STUDY TO EVALUATE EFFICACY AND SAFETY OF

“VIRACIDE”

IN THE MANAGEMENT OF

CORONA VIRUS DISEASE 2019 (COVID-19)

Version No. – 01

Dated: 04th June 2020

Protocol ID – NS-VC-CT01-20

Clinicaltrial.gov ID: NCT04596085

Confidential & Proprietary

the unauthorized use, disclosure, distribution or copying of these information is strictly prohibited

Confidential

Page

1 of 11

Table of Contents

[1 Definitions](#)

[2 Objectives](#)

[3 Analysis Sets](#)

[4 Data handling](#)

[5 Statistical methods](#)

[5.1 Descriptive methods](#)

[5.2 Primary analysis](#)

[5.3 Analysis of the secondary endpoints](#)

[5.4 Safety and/or further analyses](#)

[6 Listings, tables, figures](#)

[7 Graphs](#)

[8 Software](#)

Confidential & Proprietary

the unauthorized use, disclosure, distribution or copying of these information is strictly prohibited

Confidential

Page

2 of 11

1 Definitions

The following abbreviations will be used in this statistical analysis plan.

ITT	Intention-to-treat
PP	Per protocol
IP	Investigational product
AE	Adverse Event
SAE	Serious adverse event
TTCI	Time to clinical Improvement
SPO2	Oxygen saturation
ICU	Incentive Care Unit

Confidential & Proprietary

the unauthorized use, disclosure, distribution or copying of these information is strictly prohibitea

2 Objectives

Primary Efficacy Endpoint:

1. TICI using NEWS Score [Time Frame: First treatment date up to when PCR is negative]

The median time in days from the start of treatment with the study drug / placebo to the persistent achievement of all of the following criteria:

- Stopping a fever (which is defined as a decrease in axillary temperature below 37 ° C without the use of antipyretic drugs);
- Respiratory rate <22 / min;
- Oxygen saturation (SPO2) > 95% when breathing in atmospheric air. Measured using pulse oximetry
- Systolic blood pressure ≤200 mmHg
- Pulse rate 51-90 beats/minute
- Is conscious and alert

[Note: Persistent achievement means the preservation of each of the criteria for at least 7 days.]

2. TTIC using 7-point ordinal scale
3. Rate of progression to severe/critical COVID-19 disease based on NEWS score [Time frame: First treatment date up to 28 days]
4. Rate of progression to severe/critical COVID-19 disease based on 7-point ordinal scale [Time frame: First treatment date up to 28 days]

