5. Time to COVID-19 nucleic acid testing negativity in oropharyngeal/nasal swab) [Time Frame: First treatment date up to 28 days]

Confidential & Proprietary

The unauthorized use, disclosure, distribution or copying of these information is strictly prohibited

Secondary Efficacy Endpoints:

1. Incidence of ICU admissions [Time Frame: 28 days]
2. Subject survival rate [Time Frame: 28 days]
3. Incidence of mechanical ventilation [Time Frame: First treatment date up to 28 days]
4. Time to COVID-19 nucleic acid testing negativity in oropharyngeal/nasal swab) [Time Frame: Days 1, 7, 15]
5. Change in clinical or laboratory assessment of comorbid condition [Time Frame: First treatment date up to 28 days]
6. Percent of participants with worsening comorbid condition [Time Frame: First treatment date up to 28 days]

Safety Endpoints

1. Proportion of subjects in the treatment arm who had AE, SAE
2. Proportion of subjects in the placebo arm who had AE, SAE

Confidential & Proprietary

Any unauthorized use, disclosure, distribution or copying of these information is strictly prohibited

3 Analysis sets

Per protocol subset (PP)

Subjects without any Major protocol violation would be included in the per-protocol population, including those subjects who have completed all the visits, who did not take any prohibited medications during the study period and whose CRF was completed as requested.

Modified Intention to treat subset (mITT)

The term “mITT” includes all randomized subjects who met all inclusion/exclusion criteria, administered at least one dose of assigned product with at least completed one visit will be included in the mITT population.

Safety analysis subset

The safety population will consist of all subjects enrolled in the study, who have received at least one dose of study products i.e. mITT population.

Methods of Analysis

Primary Efficacy and secondary endpoints will be analyzed using the PP & mITT population. And Safety variables as per mITT only.

4 Data Handling

Data entry into CRF must be performed as per general CRF data entry guidelines, summarized at the time of data entry feasibility training. Data entry will be made as per source document without interpretation or modification to maintain consistency and accuracy of the data. Study specific

Confidential & Proprietary

Any unauthorized use, disclosure, distribution or copying of these information is strictly prohibited

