5.1 Descriptive methods

Participant Disposition

Demographic and Baseline Information

Continuous variables that are Age, weight, BMI, and other demographical characteristics will be summarized by overall using summary statistics i.e. the number of observations, mean and standard deviation with 95% CI (among normal distribution) or median with range (if non-normal distribution). Categorical values like gender and clinical Examination will also be summarized using frequencies and percentages.

Confidential & Proprietary

Any unauthorized use, disclosure, distribution or copying of these information is strictly prohibited

The medical history and Physical examination will be presented using frequencies and percentages of subjects for the Safety population. For continuous data student analysis of variance test and for categorical data Chi square test will be estimated to compare the baseline demographical data between groups and changes during the follow up.

5.2 Efficacy Parameters:

Summary of efficacy parameters – the number of observations, mean and standard deviation with 95% CI (among normal distribution) or median with range (if non-normal distribution)

Analysis of Primary Efficacy Parameters

In this study median Time to Clinical Improvement (TTCI) using NEWS Score [Time Frame: First treatment date up to when PCR is negative] TTIC using 7-point ordinal scale [Time Frame: First treatment date up to when PCR is negative] will be assessed for both Test and Placebo group and compare the mean time between two arms by using Mann Whitney U test.

Other variables that are Rate of progression to severe/critical COVID-19 disease based on NEWS score and 7 point ordinal scale [Time frame: First treatment date up to 28 days] will be compared by using Chi Square test.

Other parameter like Time to COVID-19 nucleic acid testing negativity in oropharyngeal/nasal swab) [Time Frame: First treatment date up to 28 days] will be estimated by Student t test or one way analysis of variance. If data is

Confidential & Proprietary

Any unauthorized use, disclosure, distribution or copying of these information is strictly prohibited

not passing normality for continuous variable Mann Whitney test will be assessed instead of student t test.

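### Five primary endpoints are each tested in two unranked populations with no success rule, testing order or alpha allocation, and the single 80% power, 5% statement is tied to none of them

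*SAP*

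**What the plan says.** The protocol synopsis (Primary Endpoints) and SAP 2 (Objectives) list the same five items: time to clinical improvement by NEWS, the same by the 7-point ordinal scale, progression by NEWS, progression by the ordinal scale, and time to a negative swab. The protocol heading is plural; the SAP heading is singular, "Primary Efficacy Endpoint", but all five are numbered under it.

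SAP 5.2 (Efficacy Parameters) tests every item between arms:
- for the two improvement times, the plan is to "compare the mean time between two arms by using Mann Whitney U test";
- a second group, introduced as "Other variables that are Rate of progression to severe/critical COVID-19 disease based on NEWS score and 7 point ordinal scale", gets a chi-square test;
- time to a negative swab gets a t test or analysis of variance, or Mann-Whitney if not normal.

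SAP 3 (Methods of Analysis) sets the populations: "Primary Efficacy and secondary endpoints will be analyzed using the PP & mITT population". Neither is called primary or supportive.

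The one statement of error and power is in the protocol synopsis (Statistical Analysis): 112 completers are "needed to assess the study objective at 80% power and 5% level of significance". The only primary objective is "To evaluate the efficacy of “ViraCide” in the management of mild COVID-19 disease". The SAP gives no significance level and has no sample-size section.

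**The concern.** A reader cannot tell from these documents what result would make the trial positive. Five endpoints in two populations make ten primary comparisons, and the plan does not say whether one, some or all must be significant, or in which population. The 5% and the 80% describe the trial only once that rule is fixed. If any one success counts, the false-positive risk generally exceeds 5%. If every endpoint must succeed, power falls below 80% unless each endpoint has more than 80% on its own. A rule settled after unblinding would also be hard to defend as prespecified.

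**Working it through.** **Inputs from the documents.** Five primary endpoints; two populations; 5% and 80%; 56 completers and 62 enrolled per arm.

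**Assumptions.** Two-sided 5% per test; equal correlation ρ between endpoint test statistics of 0.5, 0.7 or 0.9; PP–mITT correlation r of 0.9, with 0.8 as a check. If PP is a nested share f of mITT, r is roughly √f, so 0.9 corresponds to f = 0.81 and 0.8 to f = 0.64.

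**1. The plan's own figure.** 112 × 1.10 = 123.2, rounded up to 124 (56 × 1.10 = 61.6, so 62 per arm), as stated. Dividing instead gives 112 / 0.90 = 124.4, or 125, which is no material difference. The 112 itself cannot be reproduced, because no endpoint, test, effect size, variability or sidedness is given. Solving n = 2(z₀.₉₇₅ + z₀.₈₀)²/d² backwards gives d = 2.802 × √(2/56) = 0.529. This is what 56 per arm would mean if a two-sided comparison of means had been intended.

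**2. Any one endpoint may carry the claim.** For independent tests in one population, 1 − 0.95⁵ = 22.6%. For correlated tests the quantity is P(max|Zⱼ| > 1.96), obtained by multivariate-normal simulation. The three-test rows cover the case where progression is so rare that its two tests add almost nothing. At a 1% rate with 56 per arm, the chi-square test rejects only 0.28% of the time under the null.

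| Rule | ρ = 0.5 | ρ = 0.7 | ρ = 0.9 |
|---|---|---|---|
| One population, five tests | 18% | 15% | 10% |
| One population, three tests | 13% | 11% | 8% |
| Either population, five tests (r = 0.9) | 25% | 20% | 14% |
| Either population, three tests (r = 0.9) | 17% | 15% | 12% |
| Same endpoint in both, five tests (r = 0.9) | 12% | 9% | 6% |
| Same endpoint in both, three tests (r = 0.9) | 8% | 7% | 5% |

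With r = 0.8, the both-populations rule gives about 6%, 5% and 4% for three tests, and about 5% for five tests at ρ = 0.9. Counting only false claims of benefit roughly halves the one-population figures, to 5–9% for five tests and 4–6% for three, against 2.5% for a single two-sided 5% test.

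**3. All five must succeed.** With each endpoint at 80% power, joint power is 0.8⁵ = 33% if independent, and 51%, 59% and 69% at ρ = 0.5, 0.7 and 0.9.

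**4. Population behind the power statement.** The 56 per arm are completers. Completing all visits is a PP condition in SAP 3; mITT needs only eligibility, one dose and one visit. For a t test with 80% power at two-sided 5%, the detectable standardised difference is about 0.53 with 56 per arm and 0.51 with 62 (exact t; the normal approximation for 62 is 2.802 × √(2/62) = 0.503).

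**5. Cost of splitting alpha.** An endpoint with 80% power at 5% and 56 per arm has 58% at 1%. Regaining 80% takes 84 completers per arm.

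**The case against.** - **The SAP hints at a lead endpoint.** Its heading is singular, and SAP 5.2 labels progression and swab time as other variables. That is a hint, not a hierarchy: all five sit under the heading and the protocol's is plural. Even on that reading, two improvement endpoints share the lead unranked. Any-win error is then 9%, 8% and 7% at ρ = 0.5, 0.7 and 0.9 in one population, and 13%, 12% and 10% if either population may count (r = 0.9).
- **The ampersand may mean that both populations must agree.** This is a natural reading and it stands in part. Under it the error is much smaller and can reach 5% or less. But the SAP does not say so, and the reading still leaves open which endpoints must succeed.
- **The endpoints overlap and progression may be rare.** Both are true, and both are in the ranges above. A reader might multiply out ten independent tests (1 − 0.95¹⁰ = 40%). The documents do not support that figure, because PP is nested in mITT and the endpoints describe the same illness.
- **Everything will be shown.** SAP 6 lists a table for each of the five endpoints and SAP 3 commits to both populations. A reader might infer that unfavourable results could be hidden. The documents do not support that: a chosen headline could be seen beside the others.
- **The protocol supplied reads as a synopsis.** The basis for 112 may exist in a fuller text. A reader should not conclude that the sample size is wrong or was never justified, only that these documents do not connect it to an endpoint.

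**Conclusion.** The point holds: five primary endpoints, two unranked populations, and no success rule, testing order or alpha allocation. The gap is an undeclared decision rule, not concealment.

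Its size is conditional on that rule. If any endpoint may win, the chance of at least one false positive is about 10–18% in one population (8–13% with rare progression). It is 14–25% (12–17%) if either population may count. It is about 5–12% if the same endpoint must win in both, falling to about 4–5% when endpoints are highly correlated or PP and mITT agree less closely. It would be too strong to say that error exceeds 5% on every reading. If all five must succeed, error is controlled and the shortfall is in power, at 51–69%. All these figures rest on assumed correlations, two-sided 5% per test and, for power, 80% on each endpoint.

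Confidence is high on the missing rule and ranking. It is lower on the power statement, where only a synopsis is available.

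**What to change.** Before unblinding, state in both the protocol and the SAP:

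1. **One primary population**, for example mITT, with PP as a sensitivity analysis that cannot carry a claim alone. Note that mITT as defined drops randomised subjects who turn out to be ineligible. Splitting alpha does not replace this step: with Bonferroni at 1% each and either population allowed to count, overall error is still about 6% at ρ = 0.5 and r = 0.9.
2. **One success rule.** Preferred: one named primary endpoint at two-sided 5%, with the other four tested after it in a fixed order or by Holm. Alternative: Holm across all five.
3. **A restated power sentence** for that endpoint, test and population. The 0.53 and 0.51 above illustrate a t test on roughly normal data. Scores are scheduled only at screening and Days 1, 7 and 15, so time endpoints may take few distinct values, and power should be recomputed for the test actually used.

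**Cost.** Wording only, with no extra patients under the preferred rule. The downside is that fewer endpoints can support a headline claim. A five-way Bonferroni split would cost more: the drop from 80% to 58% power per endpoint shown above, or 84 instead of 56 completers per arm.

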5.0 Statistical methods

Normality Assessment – Data will be checked for normal distribution using Shapiro Wilk test.

5.1 Descriptive methods

Participant Disposition

Demographic and Baseline Information

Continuous variables that are Age, weight, BMI, and other demographical characteristics will be summarized by overall using summary statistics i.e. the number of observations, mean and standard deviation with 95% CI (among normal distribution) or median with range (if non-normal distribution). Categorical values like gender and clinical Examination will also be summarized using frequencies and percentages.

Confidential & Proprietary

Any unauthorized use, disclosure, distribution or copying of these information is strictly prohibited

The medical history and Physical examination will be presented using frequencies and percentages of subjects for the Safety population. For continuous data student analysis of variance test and for categorical data Chi square test will be estimated to compare the baseline demographical data between groups and changes during the follow up.

5.2 Efficacy Parameters:

Summary of efficacy parameters – the number of observations, mean and standard deviation with 95% CI (among normal distribution) or median with range (if non-normal distribution)

Analysis of Primary Efficacy Parameters

In this study median Time to Clinical Improvement (TTCI) using NEWS Score [Time Frame: First treatment date up to when PCR is negative] TTIC using 7-point ordinal scale [Time Frame: First treatment date up to when PCR is negative] will be assessed for both Test and Placebo group and compare the mean time between two arms by using Mann Whitney U test.

Other variables that are Rate of progression to severe/critical COVID-19 disease based on NEWS score and 7 point ordinal scale [Time frame: First treatment date up to 28 days] will be compared by using Chi Square test.

Other parameter like Time to COVID-19 nucleic acid testing negativity in oropharyngeal/nasal swab) [Time Frame: First treatment date up to 28 days] will be estimated by Student t test or one way analysis of variance. If data is

Confidential & Proprietary

Any unauthorized use, disclosure, distribution or copying of these information is strictly prohibited

not passing normality for continuous variable Mann Whitney test will be assessed instead of student t test.

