Visits of Assessment	
Screening and 3 visits and one telephonic follow-up
 
Screening Inclusion/Exclusion Criteria, Subject Inform Consent, Demography, Medical History, Physical Examination, Vital Signs, HIV; HBsAg; HCV; Hs-CRP; Pulse oximetry; NEWS scoring; 7- point ordinal scoring; Medication list review (medications being taken for comorbid conditions), Lab assessment; Urine analysis Note: Patients who do not meet the study inclusion exclusion criteria during screening should not be randomized into the study.
 
Day 1 Randomization, Vital Signs, Pulse oximetry, AE/SAE, Concomitant Medication, ViraCide/ Placebo treatment start, NEWS scoring; 7-point ordinal scoring
 
Day 7 Physical Examination, Vital Signs, AE/SAE, Concomitant Medication, ViraCide/ Placebo Compliance check, Pulse oximetry; NEWS scoring; 7-point ordinal scoring. (Note: If the subject is discharged on this day as per PI's discretion and patient's health condition then assessment scheduled for day 15 will be carried out on discharge day).
 
Day 15 Physical Examination, Vital Signs, AE/SAE, Concomitant Medication, ViraCide/ Placebo treatment end, RT-PCR for

	
Sars- Co-V2, Hs-CRP, Safety Lab Tests, Pulse oximetry; NEWS scoring; 7-point ordinal scoring, ViraCide/ Placebo Compliance check, Lab assessment including urine analysis
 
Day 28 Phone call follow up for time :
 
 • until negative RT-PCR for Sars-Co- V2, COVID-19 related mortality, • development of any COVID-19 symptom, • development of any worsening of comorbid condition; • Development of new AE/SAE; Resolution status of previous AE/SAEs 
Note: If subject is discharged before Day 15 on PI's discretion as per patients health condition, then assessments scheduled for Day 15 will be carried out on the discharge day (as far as possible and those not performed will be noted on appropriate CRF page) and Day 15 visit will be done telephonically.

Laboratory Investigations	
Screening: Recording RT-PCR- Sars-Co-V2 result; Urine pregnancy test; HIV; HBsAg; HCV; Hs-CRP; Hematology* + Biochemistry + Urine analysis*; ECG
 
Day 1: No labs
 
Day 7: No labs
 
Day 15: Oropharyngeal/nasal swab for PCR- Sars-Co-V2; Hematology* + Biochemistry + Urine analysis*; ECG; Serological biomarker: Hs-CRP

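### SAP 5.2 closes both time-to-improvement windows at PCR negativity, with no rule for subjects not yet improved, so faster viral clearance alone can bias these primary comparisons in either direction

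*SAP*

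**What the plan says.** - **Window, 7-point scale.** The Protocol synopsis (Primary Endpoints, item 2) and SAP section 2 list only "TTIC using 7-point ordinal scale", with no time frame. SAP 5.2 (Analysis of Primary Efficacy Parameters) is the only place that sets one: "TTIC using 7-point ordinal scale [Time Frame: First treatment date up to when PCR is negative".
- **Window, NEWS.** The same sentence of SAP 5.2 has "median Time to Clinical Improvement (TTCI) using NEWS Score [Time Frame: First treatment date up to when PCR is negative", and SAP section 2 item 1 agrees. The Protocol instead runs this endpoint "First treatment date up to discharge day".
- **PCR negativity is also an endpoint.** Primary endpoint 5 is "Time to COVID-19 nucleic acid testing negativity in oropharyngeal/nasal swab) [Time Frame: First treatment date up to 28 days".
- **Test.** SAP 5.2 will "compare the mean time between two arms by using Mann Whitney U test". No censoring, ranking or exclusion rule is given for a subject who is PCR-negative but not yet improved.
- **Timing of PCR.** Under Laboratory Investigations the Protocol schedules no labs on Days 1 and 7. Its only on-study swab is on Day 15: "Oropharyngeal/nasal swab for PCR- Sars-Co-V2; Hematology". Day 28 is a telephone call. A SAP secondary endpoint implies more swabs: "Time Frame: Days 1, 7, 15".
- **Timing of scores.** NEWS and 7-point scores are scheduled at screening and Days 1, 7 and 15. If a subject is discharged early, the Day 15 assessments move to the discharge day as far as possible and Day 15 is done by telephone.

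**The concern.** Follow-up for two primary endpoints ends at an event that defines a third and that the drug may bring forward. If the drug speeds clearance, its arm is watched for clinical improvement for a shorter time than placebo. The arms are then no longer compared over the same period, even when their clinical course is identical.

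Take a subject who clears virus on Day 9 and would improve on Day 12. With slower clearance this subject contributes a time of 12. Under the PCR window the subject contributes nothing if dropped, 9 if given the window-end day (3 days too early), or the worst rank if treated as a failure. The SAP does not choose among these.

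At stake is whether the two clinical endpoints can be read as evidence separate from the virological one. Making the Protocol and SAP agree on the PCR window would not solve this, because the window itself depends on an outcome.

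**Working it through.** **Inputs from the documents.** 112 completers (56 per arm), 10% dropout, 124 enrolled, 5% level (sidedness not stated; two-sided assumed), Mann-Whitney, and the visit and swab days above.

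**The plan's own figure.** 112 × 1.10 = 123.2, rounded up to 124, so the enrolled number is reproduced (112 / 0.90 = 124.4 would give 125). The 112 cannot be checked because no effect size is given. The point does not rest on it.

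**Inputs assumed.** The documents give no improvement or clearance times, so every rate below is illustrative.

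**Direction, by hand.** Let improvement and clearance be independent and exponential with medians m_i and m_c. Take m_i = 7 days in both arms (no clinical effect) and m_c = 14 on placebo, 10 on drug.

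- Share improving before the window closes = m_c / (m_c + m_i). Placebo 14/21 = 66.7%; drug 10/17 = 58.8%.
- Median recorded time, with non-improvers dropped or given the window-end day (the two coincide in this model) = m_i × m_c / (m_i + m_c). Placebo 98/21 = 4.67 days; drug 70/17 = 4.12 days.

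Dropping these subjects, or using the window-end day, makes the drug look 4.67 − 4.12 = 0.55 days faster. Ranking them as failures makes it look worse, 58.8% v 66.7% improved. The true medians are equal.

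**Size, model A.** Lognormal times, 56 per arm. Improvement median 8 or 10 days in both arms (log SD 0.6); PCR median 14 on placebo and 10 on drug (log SD 0.4); correlation 0 to 0.5. Two-sided 5% Mann-Whitney, so nominal is 2.5% per side. In the second and third rows, scores are taken only on Days 7 and 15.

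| Negativity dated by | Dropped: drug falsely better | Window-end day: drug falsely better | Worst rank |
|---|---|---|---|
| Exact date | 18-27% | 11-39% | drug falsely worse 15-36% |
| Days 7, 15, 28 | 4-5% | 11-30% | 6-11% two-sided, mostly against drug |
| Days 15, 28 | near nominal | 5-9% | near nominal (4-6% two-sided) |

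**Size, model B.** Exponential, independent times, 56 per arm, 2,000 runs per scenario. Improvement median 5, 7 or 10 days; PCR medians (placebo v drug) 10 v 7, 12 v 6 or 14 v 10.

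| Negativity dated by | Dropped: drug falsely better | Window-end day: drug falsely better | Worst rank: drug falsely worse |
|---|---|---|---|
| Daily | 6-18% | 7-40% | 6-21% |
| Days 7, 15, 28 | 4-14% | 3-15% | 4-11% |
| Days 15, 28 | 3-7% | 2-5% | 2-3% |

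**Why the last rows are small.** On the Protocol's schedule the swab and the last score fall at the same visit, so closing the window there removes no scheduled score. The main distortion left in model A comes from assigning the window end: a non-improver gets 15 if PCR-negative on Day 15 and 28 if still positive.

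**Check of the fix.** With a fixed window that ignores PCR and a common worst rank for non-improvers, false results return to about 2-3% per side, whether the window ends on Day 15 or Day 28.

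**Limit.** Neither model includes the 7-day persistence condition in the NEWS definition, so the figures apply most directly to the 7-point endpoint.

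**The case against.** The strongest reply is that the harm needs a PCR-negativity date finer than the Protocol collects. With one swab on Day 15 and a call on Day 28, the window rarely closes before the last score, and the error is near nominal under most handling rules. This largely stands, and it limits the size. It does not remove the point. The SAP names Days 1, 7 and 15 for PCR and analyses time to negativity as a continuous variable, so it expects finer dates. Early discharge also moves the swab forward, so windows can close on different days for different subjects.

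A reader might infer that the window always flatters the drug and turns a viral effect into apparent clinical benefit. The documents do not support that. It follows only if non-improvers are dropped or given the window-end day. The SAP tabulates mean times, which need a number for each subject and so make those two readings plausible. But it states no rule, and worst ranking, an ordinary choice, reverses the direction.

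It could also be said that censoring at PCR negativity with a log-rank test would suffice. In model B that gives about 2-3% per side, but only because improvement and clearance are assumed independent. The SAP plans no such analysis.

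**Conclusion.** The point holds in this form: SAP 5.2 ends both time-to-improvement windows at an outcome treatment may affect and does not say how subjects not yet improved are counted. Faster clearance alone can then bias either comparison, in a direction set by the missing rule.

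Under model A with PCR medians 10 v 14 days, the drug falsely wins in about 11-39% of trials when the negativity date is known, or falsely loses in about 15-36% under worst rank. With PCR on Days 7, 15 and 28 it falsely wins in about 11-30% if the window end is assigned and about 4-5% if non-improvers are dropped. On the Protocol's own schedule it is near nominal, except about 5-9% if the window end is assigned.

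The larger figures should not be quoted as this trial's risk. They rest on assumed improvement and clearance times and on PCR dates that the Protocol does not schedule. The case for acting is that these are primary endpoints, the direction is left open, and the correction is cheap.

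**What to change.** Before unblinding:

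1. In SAP 5.2 remove the PCR-negativity clause from both the 7-point and the NEWS endpoint, and from the NEWS item in SAP section 2. State that a negative PCR does not end observation.
2. Set one window for all subjects, from first dose to the last scheduled score (Day 15). Put the same window in the Protocol's 7-point item, which has none.
3. For NEWS, reconcile this with the Protocol's discharge-day window. Discharge also follows randomisation and can depend on outcome, so adopting it unchanged would keep a subject-specific window. State whether the 7 days of persistence must fall inside the window; if so, with a Day 15 end the latest qualifying start is about Day 15 − 7 = Day 8.
4. Give every subject not improved by the end of the window, in either arm, a common worst rank in the Mann-Whitney test. Replace the mean times in SAP section 6 with medians and the percentage improved, since a worst rank has no mean.
5. State one rule, the same in both arms, for subjects discharged before Day 15: whether the discharge-day score stands for Day 15, and whether the telephone contact can supply a score.

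The cost is SAP wording, a matching line in the Protocol and a little analysis work. No new visits or samples are needed. Item 5 takes the most thought, because early-discharged subjects have no in-person Day 15 score.
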